### 9.2 Analysis Variables

#### 9.2.1 Demographic and baseline characteristics

The baseline value is defined as the last available value before the first injection of study drug. The following demographic and baseline disease characteristics will be summarized by treatment, by study center and overall for the randomized and treated population.

Demographic characteristics are defined as follows:

- Age (in years) to be derived as:  $(\text{date of informed consent} - \text{date of birth})/365.25$
- Gender (male/female)
- Body weight (kg)
- Body Mass Index (BMI,  $\text{kg}/\text{m}^2$ ):  $\text{weight in kg}/(\text{height in meters})^2$
- Race

Disease characteristics including:

- Disease duration (years):  $(\text{date of informed consent} - \text{date of diagnosis})/365.25$
- APO-E genotype
- Baseline scores of ADAS-Cog, MMSE, ADCS-ADL, CDR/CDR-SB, and NPI
- 18F-AV-45 retention (SUVR)

Physical examination, medical history and concomitant disease, previous and concomitant medication, and HIS score will be described at baseline.

The baseline safety data of clinical chemistry and hematology, CRP, ESR, TNF- $\alpha$ , IL-6, IL-8, and number of microhemorrhages in the brain will also be summarized.

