15. Received blood or blood derivatives treatment within 3 months prior to screening.

16. Positive serology for hepatitis B virus (HBV), hepatitis C virus (HCV), or human immunodeficiency virus (HIV).
17. Current or recent participation (within 12 months before screening) in any procedures involving radioactive agents such that radiation exposure of the subject in any given year would exceed the whole-body limits of annual and total dose commitment of 5 rems set forth in the US Code of Federal Regulations (CFR) Title 21 section 361.1.
18. Abnormal clinical laboratory values as listed below, and determined to be clinically significant by the investigator at the screening:
  - Serum antinuclear antibody (ANA) >1:80
  - Rheumatoid factor (RF) result is  $\geq 17$  IU/mL
  - Platelets <150,000 or >500,000/mm^3
  - White blood cells (WBC) <3,000 or >10,500/mm^3
  - Absolute neutrophil count (ANC) <1,500/mm^3
  - Prothrombin time (PT) <9 or >13 seconds
  - Activated partial thromboplastin time (aPTT) <26.9 or >36.3 seconds
  - Serum creatinine >2 mg/dL
  - Glycosylated hemoglobin (HbA1c) >8.5%
  - Erythrocyte sedimentation rate (ESR)  $\geq$  age-adjusted upper limit of reference range (ULRR), i.e. over 50 years old: male  $\geq 20$  mm/hr, female  $\geq 30$  mm/hr; over 85 years old: male  $\geq 30$  mm/hr, female  $\geq 42$  mm/hr
  - C-reactive protein (CRP) >0.5 mg/dL
  - Aspartate aminotransferase (AST) >84 U/L
  - Alanine aminotransferase (ALT) >80 U/L

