#### 7.1.6 Safety laboratory

The following laboratory data are collected:

- Hematology: complete blood count including differential cell count and absolute neutrophil count at the first screening (S1) and every visit throughout the study (V1 to V13).
- Clinical chemistry: HbA1c at the first screening (S1); glucose AC, AST, ALT, bilirubin, sodium, total protein, BUN, creatinine, potassium, and albumin at the first screening (S1) and every visit throughout the study (V1 to V13).
- Inflammatory parameters: RF and ANA at the first screening (S1); CRP and ESR at the first screening (S1), and at Weeks 4 (V2), 16 (V4), 28 (V6), 40 (V8), 52 (V10), and 64 (V12); TNF- $\alpha$ , IL-6, and IL-8 at Weeks 0 (V1), 4 (V2), and 64 (V12).

For visits that UB-311 or placebo is scheduled to be administered (V1, V2, V3, V5, V7, V9, and V11), blood samples will be collected before the treatment.

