6. Inflammatory parameters: RF and ANA (for S1 only); CRP and ESR: for S1, V2 (Week 4), V4 (Week 16), V6 (Week 28), V8 (Week 40), V10 (Week 52), and V12 (Week 64); TNF- $\alpha$ , IL-6, and IL-8: for V1, V2 (Week 4), and V12 (Week 64).
  7. For females with childbearing potential.
  8. 30-60 minutes after injection. Vital sign: not need to measure body weight.
  9. Criteria are screened at S1. Subjects meeting inclusion criteria 1 to 14 and none of the exclusion criteria are eligible for the S2. S1 and S2 should be done within 6 weeks before V1.
- \* Blood or CSF specimens should be drawn before the UB-311/Placebo injection.

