### 8.3 Blood Sample Collection

For visits that UB-311 or placebo is scheduled to be administrated (V1, V2, V3, V5, V7, V9, and V11), blood samples will be collected before the treatment.

Visit	S1	V1	V2	V3	V4	V5	V6	V7	V8	V9	V10	V11	V12	V13
Week	-6~0	0/BL	4	12	16	24	28	36	40	48	52	60	64	78/ET
Day	-42~0	0	28±3	84±3	112±3	168±3	196±3	252±3	280±3	336±3	364±3	420±3	448±3	546±7
Vaccination		X	X	X		X		X		X		X		
Clotted Blood														
HIV, HCV, HBsAg, RF, ANA and serum pregnancy test 	5 mL													
Clinical chemistry  except HbA1c and Glucose AC, CRP 	5 mL	5 mL	5 mL	5 mL	5 mL	5 mL	5 mL	5 mL	5 mL	5 mL	5 mL	5 mL	5 mL	5 mL
TNF- $\alpha$ , IL-6, and IL-8		3.5 ml	3.5 ml										3.5 ml	
Anti-A $\beta$ , and anti- A $\beta$ 1-42 monomer and oligomer 		2 mL	2 mL	2 mL	2 mL	2 mL	2 mL	2 mL	2 mL	2 mL	2 mL	2 mL	2 mL	2 mL
EDTA Blood														
Hematology  and HbA1c 	3 mL	3 mL	3 mL	3 mL	3 mL	3 mL	3 mL	3 mL	3 mL	3 mL	3 mL	3 mL	3 mL	3 mL
ESR	3 mL		3 mL		3 mL		3 mL		3 mL		3 mL		3 mL	
APO-E genotyping		3 mL												
A $\beta$ 40/42 		2 mL	2 mL	2 mL	2 mL	2 mL	2 mL	2 mL	2 mL	2 mL	2 mL	2 mL	2 mL	2 mL
NaF Blood														
Glucose AC	2 ml	2 ml	2 ml	2 ml	2 ml	2 ml	2 ml	2 ml	2 ml	2 ml	2 ml	2 ml	2 ml	2 ml
Citrated Blood														
PT, aPTT	2.7 mL													

BL=baseline; ET=early termination

Note: In the case of testing failure, residual samples of the subject from other tests may be used for retesting.

1. Only for females with childbearing potential;
2. Clinical chemistry: AST, ALT, bilirubin, sodium, total protein, BUN, creatinine, potassium, and albumin at S1 and every visit throughout the study (V1 to V13);
3. CRP: for screening, V2 (Week 4), V4 (Week 16), V6 (Week 28), V8 (Week 40), V10 (Week 52), and V12 (Week 64);
4. For research study;
5. Hematology: complete blood count including differential cell count and ANC at S1 and every visit throughout the study (V1 to V13);
6. HbA1c: for screening only.

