#### *9.4.5.2 Analysis of laboratory variables*

The summaries will include subjects in the safety population who have at least one laboratory test performed during the post-treatment period and, when required by the definition of the abnormality, with an available baseline value and available laboratory normal ranges. For those descriptions, the baseline value will be the last available measure before the first study drug injection.

Clinical laboratory values will be converted to standard international units. Descriptive statistics will be used to summarize the laboratory results and the changes from baseline by scheduled visit for each treatment group.

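### CRP and ESR have no pre-dose sample at V1, so their baseline is the S1 eligibility value, and within-arm change from it is biased upward to the extent that criterion 18 removes high values

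*Protocol*

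**What the plan says.** **Baseline rule.** Protocol 9.2.1: "The baseline value is defined as the last available value before the first injection of study drug". Protocol 9.4.5.2 repeats it for laboratory summaries: "the baseline value will be the last available measure before the first study drug injection". SAP 4.1 and 5.12.3 carry the same rule.

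**Sampling.** Protocol 7.1.6 schedules "CRP and ESR at the first screening (S1), and at Weeks 4 (V2), 16 (V4), 28 (V6), 40 (V8), 52 (V10), and 64 (V12". The V1 blood list in 8.1.3 contains neither marker. The schedule in 8.2 has an inflammatory mark at V1, but its footnote 6 limits that mark to the cytokines ("IL-6, and IL-8: for V1, V2 (Week 4), and V12 (Week 64"). In 8.3 the ESR cell at V1 is empty, and the CRP footnote goes from screening to V2: "CRP: for screening, V2 (Week 4), V4 (Week 16), V6 (Week 28", then on to V12.

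**Entry limit.** Exclusion criterion 18 in 4.3 lists "C-reactive protein (CRP) >0.5 mg/dL" and age- and sex-specific ESR limits. It opens with a second condition: "Abnormal clinical laboratory values as listed below, and determined to be clinically significant by the investigator at the screening".

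**Use.** Protocol 9.2.1 and SAP 4.1 list CRP and ESR among the baseline data to be summarised. Protocol 9.4.5.2 and SAP 5.12.3 summarise laboratory change from baseline descriptively, by visit and treatment group, with no between-arm contrast specified.

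**The concern.** When one measurement both decides entry and serves as baseline, removing high values leaves a baseline that is low partly by chance. The next measurement drifts back up on average with no treatment effect (regression to the mean).

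The plan avoids this for the other capped markers that it follows over time. Blood counts, creatinine, AST and ALT are redrawn at V1, so their baseline is not the selection sample. The cytokines are first drawn at V1 and have no entry limit. HbA1c, RF, ANA, PT and aPTT are taken at S1 only, so no change is planned for them. CRP and ESR alone combine one-sided entry screening, planned change from baseline, and no pre-dose redraw.

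Safety is a primary endpoint, and 7.10 names post-vaccination meningoencephalitis as the risk carried over from an earlier vaccine. Every scheduled post-baseline CRP and ESR sample falls four weeks after an injection visit. A rise created by selection would therefore appear exactly where a reader looks for vaccine-related inflammation, and the schedule provides no unselected pre-dose value to separate the two.

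**Working it through.** The documents state no figure on this point, so there is none to reproduce.

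**Step 1: which sample is the baseline.** The V1 cells are empty for both markers, so the last scheduled value before the first injection is S1. Protocol 8.1.1 allows S1 up to 42 days before randomization. An unscheduled repeat before dosing would replace S1 under the same rule.

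**Step 2: size for CRP.** The limit L = 0.5 mg/dL is from 4.3. Everything else is assumed:

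- log-normal CRP, with the same distribution at S1 and at the later visit if nobody is excluded
- log-SD s = 1.0 and median m = 0.10 to 0.20 mg/dL
- correlation r = 0.5 to 0.6 between log values at S1 and later
- q, the share of above-limit subjects actually excluded, from 0 to 1

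Let c = ln(L/m)/s and let Φ be the normal distribution function. Among those enrolled, with no drug effect:

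later mean / baseline mean = [1 − q·Φ(r·s − c)] / [1 − q·Φ(s − c)]

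Low end (m = 0.10, r = 0.6): c = ln 5 = 1.609, Φ(0.6 − 1.609) = 0.1564, Φ(1 − 1.609) = 0.2711.

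- q = 1: 0.8436/0.7289 = 1.157
- q = 0.25: 0.9609/0.9322 = 1.031

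High end (m = 0.20, r = 0.5): c = ln 2.5 = 0.916, Φ(0.5 − 0.916) = 0.3386, Φ(1 − 0.916) = 0.5334.

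- q = 1: 0.6614/0.4666 = 1.417
- q = 0.5: 0.8307/0.7333 = 1.133

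The same formula gives the whole grid (rise in mean CRP):

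| Median, r | q = 0 | q = 0.25 | q = 0.5 | q = 1 |
|---|---|---|---|---|
| 0.10, 0.6 | 0% | 3.1% | 6.6% | 15.7% |
| 0.10, 0.5 | 0% | 3.7% | 8.0% | 18.9% |
| 0.15, 0.6 | 0% | 4.1% | 9.3% | 25.2% |
| 0.15, 0.5 | 0% | 5.0% | 11.3% | 30.7% |
| 0.20, 0.6 | 0% | 4.5% | 10.7% | 33.7% |
| 0.20, 0.5 | 0% | 5.6% | 13.3% | 41.7% |

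So the rise is 0% with no exclusions, about 3–13% with a quarter to half excluded, and about 16–42% with all excluded.

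**Step 3: ESR.** Take the male limit of 20 mm/hr from 4.3. Assume log-SD 0.6, 10–20% of candidates above the limit, and correlation 0.4–0.8. Simulation gives a mean rise of 0 at q = 0, about 0.1–1.1 mm/hr at q = 0.25–0.5, and about 0.4–2.4 mm/hr at q = 1.

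**Step 4: would every arm show it?** Simulating arms of 15, for CRP (log-SD 1.0) and ESR with the shares and correlations of step 3, the chance that a given marker's mean change is positive in all three arms is about 29–75% at q = 1 and 15–30% at q = 0.25–0.5. At q = 0 it is 12.5% (0.5³), which is chance alone.

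**Step 5: effect of a V1 baseline.** The V1 value would not be the one screened on. If V1 and later values correlate equally with S1, selection on S1 lowers both expected values by the same amount and the expected change is zero. If the correlations differ, a smaller remainder is left.

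**The case against.** The strongest case for leaving the plan alone has four parts.

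- **The limit is discretionary.** A subject with CRP above 0.5 mg/dL can enter if the investigator does not judge the value clinically significant. The documents do not say how often that will happen, and if nobody is excluded there is no artefact. This stands, and is why the range in the working starts at zero.
- **Placebo handles it.** The summaries are by arm, alongside a concurrent randomised placebo group. The expected shift is the same in every arm, so active versus placebo is unbiased. This also stands. What remains is that the plan tabulates within-arm change and specifies no contrast, so the reader has to make the adjustment.
- **Little depends on it.** No test or stopping rule uses CRP or ESR change. Under 7.6, laboratory abnormalities become adverse events only if medically relevant. This limits the consequence to interpretation.
- **The cytokines offer an unselected reference.** True, but they are drawn only at V1, V2 and V12, and they do not supply a pre-dose CRP or ESR.

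A reader might go further and infer that both markers are certain to rise in every arm, or that the reported changes will be wrong. The documents support neither. The shift is an expectation that depends on unstated inputs, and with 15 per arm a rise in all three arms is not assured even if every above-limit subject is excluded. The change would also be computed correctly under the stated rule. Only reading it as a treatment effect within an arm is open to bias.

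**Conclusion.** The point holds as a limited one. The missing V1 sample, the S1 baseline and the direction of any bias follow from the documents. The size does not: it rests on the assumed CRP and ESR distributions, on the within-subject correlation, and above all on how many above-limit candidates are excluded. Zero is a possible value; the upper end of 42% for mean CRP needs every above-limit candidate to be excluded. Randomised comparisons are unaffected. Even without selection, a value up to 42 days old is a weaker pre-dose reference than the same-day sample that the plan takes for counts and chemistry. This is a cheap improvement to a planned safety summary and does not undermine the trial's conclusions.

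**What to change.** Add CRP and ESR to the blood drawn before injection at V1, in Protocol 7.1.6, 8.1.3, 8.2 footnote 6 and 8.3. The baseline rule needs no change: it would then take the V1 value, leaving S1 for eligibility only.

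The cost is one CRP test per subject on the 5 mL chemistry tube that 8.3 already draws at V1, plus one extra 3 mL EDTA tube per subject for ESR, about 45 tubes at the planned enrolment. No visit is added.

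A V1 sample cannot be recovered for anyone already dosed, and the documents do not give enrolment status. For those subjects, add a sentence to SAP 5.12.3: present CRP and ESR change as the difference from placebo, and label the baseline in the tables as the S1 eligibility value. That costs only text and table footnotes.

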### 9.2.2 Immunogenicity variables

The level of anti-A $\beta$  antibodies is one of the primary endpoints and is assessed at baseline (V1) and every following visit (V2 to V13). The one-sided 95% confidence interval (CI, right side) from all visits (V1 to V13) for subjects in Arm 3 (placebo group) will be calculated as the threshold of response. Antibody responders will be defined as the subjects with serum antibody titer > response threshold at any visit after baseline. Response rate will be calculated for each arm.

### 9.2.3 Efficacy variables

#### 9.2.3.1 Rating scales

ADAS-Cog, ADCS-ADL, and NPI are rated at baseline (V1), Week 28 (V6), Week 52 (V10) and Week 78 (V13), while MMSE and CDR/CDR-SB are assessed at the first screening (S1), Week 24 (V5), Week 48 (V9) and Week 78 (V13). If a patient withdraws from the study prematurely during the study period or does not have any or some of the scores, the data will be treated as missing values, and no procedure for handling missing assessments will be applied.

#### 9.2.3.2 18F-AV-45 retention

18F-AV-45 PET scanning is performed at the second screening (S2), Week 52 (V10), and Week 78 (V13). No procedure for handling missing assessments will be applied if there is a missing value.

### 9.2.4 Safety variables

The safety analysis will be based on the reported adverse events and other safety information including:

- Local tolerability at injection site
- Amyloid-related imaging abnormalities (ARIA) including vasogenic edema and/or sulcal effusion (ARIA-E) and hemosiderin deposits (ARIA-H), including microhemorrhage and superficial siderosis
- Vital signs
- Physical examination
- 12-lead ECG
- Laboratory tests: hematology, clinical chemistry (HbA1c, glucose AC, AST, ALT, bilirubin, sodium, total protein, BUN, creatinine, potassium, and albumin), and inflammatory parameters (CRP, ESR, TNF- $\alpha$ , IL-6, and IL-8)

## 9.3 Analysis Populations

### 9.3.1 Efficacy populations

The analyses of immunogenicity and efficacy endpoints will be performed by the treatment allocation and based on the modified intention-to-treat and per-protocol populations described below.

Modified intention-to-treat (mITT) population: all randomized subjects who receive at least one dose of the study drug, and have both baseline and at least one post-baseline assessment in any of the primary or secondary variables, irrespective of compliance with the study protocol and procedures.

Per-protocol (PP) population: subjects who receive all planned doses of the study drug, complete the treatment period, fulfil all entry criteria, and have no key protocol deviation.

### 9.3.2 Safety population

The safety population is the total treated population defined as all subjects randomized and exposed to at least one dose of the study drug, regardless of the amount of treatment administered.

Safety endpoints and tolerability will be analyzed based on the safety population.

### 9.3.3 Disposition of subjects

The total number of subjects for each of the following categories will be presented in the clinical study report (CSR).

- Screened subjects: all patients who have signed the informed consent
- Randomized subjects: subjects who receive a randomization number via IVRS/IWRS
- The safety population (as defined in Section 9.3.2)
- The mITT population (as defined in Section 9.3.1)
- The PP population (as defined in Section 9.3.1)

For the following two categories of subjects, counts, and percentages will be calculated for each treatment group using the number of randomized subjects in each group as denominator.

- Subjects who have completed the 60-week treatment period
- Subjects who discontinue the study drug during the treatment period

A list of subjects prematurely withdrawn from the study, along with reasons for discontinuation, will be provided.

## 9.4 Statistical Methods

Continuous data will be summarized by treatment group using the number of observations available (n), mean, standard deviation (SD), median, interquartile range (IQR), minimum, and maximum.

Categorical data will be summarized by treatment group using count and percentage. Missing data will not be categorized in the summaries.

In general, descriptive statistics of quantitative efficacy and safety parameters (results and changes from baseline) by scheduled visit will be provided on observed cases, i.e. the inclusion of only subjects with non-missing assessments at a specific visit.

All statistical tests will be two-sided at the alpha level of 0.05.

#### 9.4.1 Demographic and baseline characteristics

##### *9.4.1.1 Subject demographic characteristics, medical history and diagnoses*

Descriptive statistics will be used to summarize the demographic, baseline characteristics data and medical history for the safety population to describe the study population by study center, treatment group and overall. The distribution of demographic and baseline characteristics among three treatment groups will be evaluated using chi-square or Fisher's exact test for categorical variables and the Kruskal-Wallis test or analysis of variance (ANOVA) for continuous variables.

Pathologies associated with past medical and surgical history will be classified into primary system organ classes and preferred terms using MedDRA and will be summarized by study center, treatment group and overall using counts and percentages. The primary system organ classes and preferred terms will be sorted in decreasing order of frequency.

##### *9.4.1.2 Previous and concomitant medications/therapy*

Medications will be classified into the following two groups:

- Previous medications are those that the subject took within 24 week period prior to the first screening visit (S1) and prior to the first administration of the study drug at Week 0 (V1/baseline).
- Concomitant medications are those that the subject continued or started on or after the first injection of the study drug up to the end of the study.

These medications will be classified into anatomic and therapeutic classes using the World Health Organization (WHO) Drug Dictionary. Subject will only be counted once within each anatomic and therapeutic class.

Descriptive statistics including number of subjects and percentage will be provided. No statistical testing for between-group difference will be performed.

##### *9.4.1.3 Baseline efficacy and safety data*

For efficacy and safety analysis, the baseline for a given parameter is defined as the last available value prior to the first injection of the study medication. Baseline efficacy and safety variables will be summarized by study center, treatment group, and overall.

#### 9.4.2 Treatment tolerability and compliance

The overall treatment tolerability of UB-311 for each arm is defined as the percentage of number of administered doses divided by number of administered doses plus number of missed doses of subject(s) who drops out due to drug-related AE(s). It is calculated according to the following formula:

$$100\% \times (A+B_1+C+D) / (A+B_1+B_2+C+D)$$

where

A: number of administered doses of completers

B1: number of administered doses of subject(s) who drops out due to drug-related AE(s)

B2: number of missed doses of subject(s) who drops out due to drug-related AE(s)

C: number of administered doses of subject(s) who drops out due to drug-unrelated AE(s)

D: number of administered doses of subject(s) who drops out not due to AE(s)

The overall compliance is defined as the actual dose (UB-311 or placebo) of injection compared to the prescribed dose of treatment during the study. It is calculated according to the following formula:

$$100\% \times (\text{Actual injection dose}/\text{Prescribed injection dose})$$

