## 2 OBJECTIVES

The primary objectives of this study are to assess the safety and tolerability of two regimens of UB-311, and to evaluate the immunogenicity of two regimens of UB-311 through measurement of anti-A $\beta$  antibodies.

The secondary objectives are to evaluate the effects of UB-311 on the changes of cognitive and functional performance over a period of 78 weeks, and to investigate whether UB-311 treatment results in changes in amyloid deposition *in vivo* by 18F-AV-45 PET imaging.

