## 4 SELECTION AND WITHDRAWAL OF SUBJECTS

### 4.1 Number of Subjects

It is planned to recruit approximately 45 subjects (15 per arm) to receive study treatment in the 78-week double-blind, placebo-controlled study. The randomization procedure continues until the target number of treated patients is reached.

The screen failure rate is estimated to be 50%; therefore, to reach this number it is planned to screen at least 90 subjects.

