### 5.3 Handling of Study Drug

#### 5.3.1 Packing and Labelling

The treatment box for each subject includes 7 vials numbered in the order of injection. The boxes for Arm 1 contain 7 vials of UB-311. The boxes for Arm 2 contain 5 vials of UB-311 and 2 vials of placebo. The boxes for Arm 3 contain 7 vials of placebo. Each box and vial is labelled with the randomization code, storage condition, and manufacturer.

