## 8 STUDY PROCEDURES

### 8.1 Study Visits

The study consists of a screening period (up to 6 weeks) with 2 visits, a double-blind, placebo-controlled treatment period (60 weeks) with 11 visits, and a double-blind follow-up period (18 weeks) with 2 visits. From V2 (Week 4) to V12 (Week 64), a time frame of  $\pm 3$  days is acceptable using the day of V1 as reference (Day 0), i.e. if one visit date is changed, the next visit should take place according to the original schedule. For V13 (Week 78), a time frame of  $\pm 7$  days is acceptable using the day of V1 as reference. Out of visit/dosing window and missing visit/dose are considered as protocol deviations. Additional items for research purposes at each visit will be described in details in a separate research protocol (Appendix 2).

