5.8 Treatment Tolerability and Compliance

Overall treatment tolerability and compliance will be summarized in safety population.

The overall treatment tolerability of UB-311 for each arm is defined as the percentage of number of administered doses divided by number of administered doses plus number of missed doses of subject(s) who drops out due to drug-related AE(s). It is calculated according to the following formula:

$$100\% \times (A+B1+C+D) / (A+B1+B2+C+D)$$

where

A: number of administered doses of completers

B1: number of administered doses of subject(s) who drops out due to drug-related AE(s)

B2: number of missed doses of subject(s) who drops out due to drug-related AE(s)

C: number of administered doses of subject(s) who drops out due to drug-unrelated AE(s)

D: number of administered doses of subject(s) who drops out not due to AE(s)

The overall compliance is defined as the actual dose (UB-311 or placebo) of injection compared to the prescribed dose of treatment during the study. It is calculated according to the following formula:

$$100\% \times (\text{Actual injection dose}/\text{Prescribed injection dose})$$

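### The overall tolerability formula leaves out doses that completers miss because of drug-related AEs, so those losses cannot lower the reported percentage

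*Protocol*

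**What the plan says.** Tolerability belongs to the first objective of the trial: "The primary objectives of this study are to assess the safety and tolerability of two regimens of UB-311" (Protocol section 2). Protocol 3.2.1 and SAP 2.3 list it with safety as a primary endpoint.

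The measure is introduced as "The overall treatment tolerability of UB-311 for each arm" (Protocol 9.4.2). The synopsis and SAP 5.8 give the same formula:

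100% × (A + B1 + C + D) / (A + B1 + B2 + C + D)

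A, B1, C and D are all doses given: to completers, to dropouts for drug-related AEs, to dropouts for unrelated AEs, and to dropouts for other reasons. For completers the term reads "A: number of administered doses of completers". The formula has one term for doses not given (B2, "number of missed doses of subject(s) who drops out due to drug-related AE(s").

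The same sections define overall compliance as actual over prescribed injection dose.

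Two other places show that a subject can miss a dose and still complete. Protocol 8.1 says "Out of visit/dosing window and missing visit/dose are considered as protocol deviations", so a missed dose is a deviation and not by itself a withdrawal. The per-protocol definition (Protocol 9.3.1, SAP 5.3.1) lists receipt of all planned doses and completion of the treatment period as separate conditions.

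Neither document defines a completer or a dropout for the formula. Protocol 4.4 distinguishes withdrawal from study treatment and withdrawal from the study, and encourages withdrawn subjects to attend the remaining visits. SAP 5.3.2 counts completion of the 60-week treatment period, while SAP 5.5 counts completion of the study.

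**The concern.** A tolerability percentage should fall when doses are not given because the product was poorly tolerated. This one falls only if the subject also drops out. If a completer skips injections because of a drug-related AE, those injections disappear from the calculation, as if they had never been planned.

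The undefined terms widen the gap. A subject who stops injections for a drug-related AE but keeps attending could be classed as a completer (missed doses ignored) or as a dropout (missed doses counted). The same data then give two different results.

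What is at stake is how a descriptive figure for a primary objective is read. No test, threshold, stopping rule or sample-size argument uses it.

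**Working it through.** The plan states no expected value for this measure, so there is no figure to reproduce. The check applies the plan's own formula to assumed patterns of missed doses.

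**Inputs**
- 15 subjects per arm: "It is planned to recruit approximately 45 subjects (15 per arm) to receive study treatment" (Protocol 4.1).
- 7 injections per subject in every arm: "The treatment box for each subject includes 7 vials numbered in the order of injection" (Protocol 5.3.1). Planned doses per arm are 15 × 7 = 105.
- The number and timing of drug-related omissions and dropouts are **assumptions**; the documents give none.

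Write G = A + B1 + C + D for all doses given. The plan's measure is G/(G + B2). The corrected measure is G/(G + B2*), where B2* is every planned dose not given because of a drug-related AE, whoever missed it. B2* is never smaller than B2, so the corrected value is never higher than the plan's.

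**1. Completers who miss doses for drug-related AEs**

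| Assumed pattern | Given | Plan's formula | Corrected |
|---|---|---|---|
| 5 completers miss 2 each, no dropouts | 10×7 + 5×5 = 95 | 95/95 = 100% | 95/105 = 90.5% |
| 5 completers miss 3 each, no dropouts | 10×7 + 5×4 = 90 | 90/90 = 100% | 90/105 = 85.7% |
| 15 completers miss 3 each, no dropouts | 15×4 = 60 | 60/60 = 100% | 60/105 = 57.1% |
| 5 drug-related dropouts after dose 4, and 10 completers miss 2 each | 20 + 50 = 70 | 70/(70+15) = 82.4% | 70/105 = 66.7% |

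**2. Effect of the undefined terms**

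Three subjects stop injections after dose 4 for a drug-related AE and keep attending; the other 12 receive all 7. Doses given are 12×7 + 3×4 = 96.
- Classed as completers: B2 = 0, so 96/96 = 100%.
- Classed as dropouts: B2 = 3×3 = 9, so 96/105 = 91.4%.

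**3. Doses against subjects**

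If those three are dropouts, the dose-weighted figure is 91.4%, while 12/15 = 80% of subjects stayed on treatment (exact 95% CI 51.9% to 95.7%). Equivalently, 3/15 = 20% stopped (4.3% to 48.1%). With 5 dropouts after dose 4 the figures are 90/105 = 85.7% of doses and 10/15 = 66.7% of subjects.

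**4. How far the formula can move**

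All 15 dropping out for drug-related AEs after dose 6 gives 90/105 = 85.7%. All 15 after dose 1 gives 15/105 = 14.3%.

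**5. Arm 2: all 7 injections or the 5 active ones (15 × 5 = 75)**

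Assume 5 drug-related dropouts, all others complete.
- After injection 3: 85/105 = 81.0% counting all, 65/75 = 86.7% counting active only.
- After injection 4: 90/105 = 85.7% and 65/75 = 86.7%.
- After injection 6: 100/105 = 95.2% and 70/75 = 93.3%.

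The direction depends on when subjects leave.

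**The case against.** The strongest reply is that the missing information appears elsewhere. Compliance, defined in the same sections, counts every missed injection; in the five-completer example it is 95/105 = 90.5%, equal to the corrected figure. The plan also tabulates, per arm, subjects with treatment-emergent AEs that led to stopping treatment, AEs by causality and grade, injection-site reactions and reasons for withdrawal, and it lists protocol deviations. This stands in part. The total loss is visible, but compliance mixes drug-related omissions with all others, and the discontinuation table does not cover subjects who skip doses and continue. None of these outputs changes the tolerability percentage.

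Second, the plan describes no route for withholding a dose for a drug-related AE and then resuming, and Protocol 4.4 makes intolerable AEs due to treatment a ground for withdrawal. That is fair: how often completers would miss doses this way is unknown. Protocol 8.1 and the per-protocol definition nevertheless allow it, and the classification problem remains for subjects who stop injections and keep attending.

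Third, the measure is openly a percentage of doses, is descriptive, and uses the same rule in the placebo arm. That stands. Weighting by dose is a legitimate choice; the subject-level figure is an addition, not a correction of an error.

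A reader might go further and infer that the formula can only flatter the vaccine. Against the corrected dose-based figure it can never be too low. Against a subject-level figure it can be. Suppose 3 subjects drop out for drug-related AEs after dose 1, 5 leave for unrelated reasons after dose 1, and 7 complete. Then G = 49 + 3 + 5 = 57 and B2 = 18, giving 57/75 = 76%, below the 12/15 = 80% without a drug-related dropout.

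**Conclusion.** The defect holds, in a limited form. By construction, completers' drug-related missed doses cannot lower the tolerability percentage; with no drug-related dropouts it stays at 100% whatever completers miss. In the assumed example of five completers missing 2 doses each, the overstatement is 9.5 percentage points (100% against 90.5%). The actual size depends on how many such doses occur and on how subjects who stop injections are classed, and the documents settle neither. If no completer misses a dose for a drug-related AE and every subject who stops for one is classed as a dropout, the two versions agree.

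Two stronger readings are not supported. Values of about 86% to 100% illustrate how results can look favourable, but 86% is not a floor: early dropout takes the formula as low as 14.3%. Nor do the placebo injections in Arm 2 systematically inflate its figure; in the patterns above, counting them lowers it for dropout after injection 3 or 4 and raises it after injection 6. The Arm 2 issue is one of labelling and definition.

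The effect is confined to one descriptive measure of a primary objective. It is still worth repairing, because the rule is explicit and the repair is small.

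**What to change.** In SAP 5.8, with the same wording in Protocol 9.4.2 and the synopsis if the protocol is amended:

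1. Redefine B2 as every planned dose not given because of a drug-related AE, in completers and in dropouts.
2. Define completer and dropout for this measure, and state that a subject who stops injections for a drug-related AE but stays in follow-up counts under B1 and B2.
3. Beside the percentage, report per arm the number and percentage of subjects with any dose omitted or treatment stopped for a drug-related AE, with an exact 95% CI.
4. State whether the two placebo injections in Arm 2 count, or relabel the measure as tolerability of the assigned injections.

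The cost is a few lines of SAP text, one table row and a figure that may be less favourable. The reason for each omitted dose must be available, from the CRF or the deviation listing in SAP 5.4, and should be assigned before unblinding. No visit, dose or clinical rule changes.
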